14.1.4.3 Superiority test of the primary safety endpoint

If non-inferiority of safety of Amulet over control is demonstrated, a reflex test for superiority will be performed to determine if the Amulet device is superior to the Control device. The hypothesis is as follows:

$$H_0: p_1(\text{Amulet}) - p_1(\text{Control}) \geq 0$$

$$H_1: p_1(\text{Amulet}) - p_1(\text{Control}) < 0$$

The hypothesis will be tested at the 2.5% significance level. [REDACTED]

14.1.4.4 Superiority test of the primary effectiveness endpoint

If non-inferiority of effectiveness of Amulet over Control is demonstrated, a reflex test for superiority will be performed to determine if the Amulet device is superior to the Control device. The hypothesis is as follows:

$$H_0: p_2(\text{Amulet}) - p_2(\text{Control}) \geq 0$$

$$H_1: p_2(\text{Amulet}) - p_2(\text{Control}) < 0$$

The hypothesis will be tested at the 2.5% significance level. [REDACTED]

14.1.4.5 Superiority test of device closure rate at the 45-day visit

If non-inferiority of device closure endpoint of Amulet over control is demonstrated, a reflex test for superiority will be performed to determine if the Amulet device is superior to the Control device. The following hypothesis will be tested:

$$H_0: p_3(\text{Amulet}) - p_3(\text{Control}) \leq 0$$

$$H_1: p_3(\text{Amulet}) - p_3(\text{Control}) > 0$$

The hypothesis will be tested at the 2.5% significance level.

[Redacted text block]

[REDACTED]

[REDACTED]

[REDACTED]

[REDACTED]

[REDACTED]

[REDACTED]

[REDACTED]

[REDACTED]

[REDACTED]

[REDACTED]

[REDACTED]

[REDACTED]

[REDACTED]

[REDACTED]

[REDACTED]

[REDACTED]

[REDACTED]

[REDACTED]

[REDACTED]

[REDACTED]

[REDACTED]

15 ECONOMIC AND QUALITY OF LIFE ANALYSIS

In conjunction with the clinical trial, resource utilization and quality of life data will be collected and compared among the Amulet and Control device recipients using descriptive statistics. The economic and quality of life analysis will be fully integrated into the clinical trial.

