- Neurologic assessments (instruments include Modified Rankin Scale (mRS), Barthel Index, and National Institute of Health Stroke Scale (NIHSS) (must be performed by NIHSS- Barthel- and mRS-certified personnel)
- Questionnaire for Verifying Stroke-Free Status (QVSFS)
- CT/MRI for subjects with documented history of TIA/stroke (previous imaging done post-neurological event is acceptable; otherwise must be repeated after consent)
- 12-lead ECG
- CHADS₂ and CHA₂DS₂-VASc Score
- HAS-BLED Score
- INR assessment (INR target range 2-3) if subject on warfarin (or other oral anticoagulants requiring INR assessments)
- Medication assessment including the use of antiplatelet, and any anticoagulation medication
- Pregnancy test (required for females of childbearing potential only)
- EQ-5D-5L (Health Questionnaire)
- TEE/TOE to confirm eligibility (echoes done up to 90 days prior to consent will be accepted as baseline)

Note: Once a subject is randomized, the LAA implant procedure must occur within 14 days.

Follow-up Testing:

- Transthoracic echocardiogram (TTE) before discharge to check for device embolization or pericardial effusion
- TEE/TOE at 45-day visit
 - Perform color Doppler assessment
 - If residual jet is present around the device, measure size of residual jet around the device
 - Confirm absence of intra-cardiac thrombus
 - If closure is **not** confirmed at 45-day visit, continue oral anticoagulation (OAC, including NOACS) (Amulet subjects) or warfarin* (Control subjects) until 6-month

TEE/TOE to assess LAA seal (closure is defined as ≤ 5 mm residual jet flow around margins of the device)

- TEE/TOE at 12-month visit
- Adverse event assessment, medication assessment, and stroke ascertainment at each follow-up
- Questionnaire for Verifying Stroke-Free Status (QVSFS) (all visits)
- INR assessment (if subject is still on warfarin or other oral anticoagulants requiring INR assessments)
- EQ-5D-5L health questionnaire at 45-day and 6-, 12-, and 18- month visits

*Subjects enrolled outside the US may take other anticoagulants/vitamin K antagonists in lieu of warfarin

Medication Requirements (All Subjects)

- Aspirin (81-100 mg) 1 day prior to implant

Amulet Subjects (Post-Procedure)

- Aspirin (81-100 mg) and clopidogrel OR aspirin (81-100 mg) and OAC daily until the 45-day TEE/TOE is performed. An alternative to clopidogrel may be used if a subject is a non-responder to clopidogrel, as documented in the subject's medical record/study chart.

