5.2 Study Design and Scope

The Amulet IDE trial is a prospective, randomized, multi-center active control worldwide trial, designed to evaluate the safety and effectiveness of the AMPLATZER Amulet Left Atrial Appendage Occluder. Subjects will be randomized in a 1:1 ratio between the Amulet LAA occlusion device (treatment) or a Boston Scientific LAA closure device (Control).

All enrolled subjects will follow the protocol-required tests and assessments at each scheduled follow-up visit. At US sites or sites where the implanting physicians do not have Amulet implant experience, up to 3 subjects per sponsor-approved implanter may be implanted with the Amulet device prior to randomization as part of the Roll-In Phase, in order to provide initial experience to the site. These data will not be included in the formal endpoint analyses, while data from roll-in subjects at each site will be included in the clinical investigation report and reported to regulatory authorities. All roll-in subjects will have the same data collection and follow-up schedule as randomized subjects.

The trial will be conducted at up to 150 sites worldwide, with up to 100 sites in the US. A majority of subjects will be enrolled in the US. Data collected during this trial will be used

to support approval of the Amulet device in the United States as well as other countries, as needed.

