5.2.1 Number of Required Subjects

A total of 1878 subjects will be randomized to Amulet or Control at up to 150 sites worldwide.

Approximately 343 additional subjects are expected to be enrolled in the Roll-in Phase. Since US implanting physicians have no experience with the Amulet device, up to 3 roll-in subjects per US implanter will result in approximately 343 subjects enrolled in the Roll-in phase (assuming that 40 sites in the US will be initiated under protocol version C, with an average of 2 implanters per site, the total number of roll-in cases for the trial will be approximately 343 subjects: 103 under the previous criteria + 240 under protocol version C).

There is no minimum number of subjects to be enrolled at each site. To ensure enrollment balance across study sites, no investigational site will be permitted to enroll more than 20% of the maximum sample size for the randomized trial.

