5.3.3 Descriptive Endpoints/Outcome Measures

The following endpoints will be descriptively summarized in randomized subjects:

- Technical success rate
- Procedural success rate
- Device success rate
- Number of subjects on oral anticoagulant at each follow-up visit
- Procedure duration
- Procedural complications by operator
- Device thrombosis
- Transient ischemic attack
- Hemorrhagic stroke
- Systemic embolism
- All-cause mortality
- Cardiovascular mortality
- Major bleeding, by site and severity (defined as Type 3 based on BARC definition)
- Minor bleeding, by site and severity (Minor bleeding defined as Type 2 based on BARC)

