7.1 Screening/Enrollment/Baseline

The following baseline and enrollment activities are required as part of the screening process. All baseline activities should be done after informed consent is obtained, except where otherwise noted.

- History and physical (may be done per standard of care up to 30 days prior to consent)
- Cardiovascular and medical exam (may be done per standard of care up to 30 days prior to consent)
- Neurological exam (assessment by a neurologist for subjects with a history of TIA and/or stroke, per institutional standard of care)
- Neurologic assessment: Modified Rankin Scale (mRS), NIHSS, Barthel Index (must be performed by NIHSS-, Barthel- and mRS-certified personnel)
- Questionnaire for Verifying Stroke-Free Status (QVSFS)
- CT/MRI for subjects with documented history of TIA/stroke (previous imaging done post-neurological event per standard of care is acceptable; otherwise must be done after consent)
- 12-lead ECG (may be done per standard of care up to 30 days prior to consent)
- CHADS₂ Score
- CHA₂DS₂-VASc score
- HAS-BLED score
- INR Assessment (INR target range 2-3) if subject is taking warfarin (or other oral anticoagulants requiring INR assessments)
- Medication assessment including the use of antiplatelet and anticoagulation medication
- Pregnancy test (required for females of childbearing potential only)
- EQ-5D-5L (Health Questionnaire)
- TEE/TOE to confirm eligibility (echoes done up to 90 days prior to consent will be accepted as baseline)

The principal investigator or delegated study personnel is responsible for screening potential subjects to determine subject eligibility for the trial. Enrollment information (date of consent, inclusion/exclusion information, etc.) will be recorded in the subject's medical record and on the Baseline and Inclusion/Exclusion eCRF. Every effort must be made to submit the Inclusion/Exclusion eCRF within one week of screening.

All subjects screened (including those who sign the informed consent) for the trial should be entered onto a Screening Log. If a subject does not meet all inclusion criteria or meets any of the exclusion criteria, the subject cannot participate in the randomized trial.

If a subject is consented and undergoes study-specific testing (i.e. testing that otherwise would not be conducted unless participating in this trial) but does not qualify for the trial,

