14 STATISTICAL CONSIDERATIONS

The following section describes statistical methods for the clinical investigation and justification of the design. Additional details on statistical analyses, including sensitivity analyses, poolability analyses and analysis of descriptive endpoints, are maintained in a separate Statistical Analysis Plan (SAP).

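### Section 15 compares quality of life by descriptive statistics only and states no use of the baseline EQ-5D-5L, so the comparison is less precise than the collected data allow

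*Protocol*

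**What the plan says.** Protocol Section 15 covers quality of life in two sentences. The operative one states that "resource utilization and quality of life data will be collected and compared among the Amulet and Control device recipients using descriptive statistics". It names no summary measure, interval, model or covariate.

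The data are richer than that method requires. Protocol Section 7.1 introduces its list with "The following baseline and enrollment activities are required as part of the screening process", and the EQ-5D-5L is on that list. Section 7.3 randomizes a subject only once eligibility is settled, so the baseline form belongs to the period before allocation. The Synopsis then schedules the "EQ-5D-5L health questionnaire at 45-day and 6-, 12-, and 18- month visits". Table 3 agrees: five questionnaires per subject.

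Quality of life is not among the primary, secondary or descriptive endpoints in Protocol Sections 5.3.1 to 5.3.3 and carries no hypothesis. Protocol Section 14 refers further analysis detail to the SAP. The readable SAP text mentions neither quality of life nor the EQ-5D-5L, but parts of the SAP are blacked out.

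**The concern.** A subject's EQ-5D-5L at baseline usually predicts the same subject's later values. If the arms are compared on follow-up values alone, all of that predictable between-subject variation stays in the error term. Nor does Section 15 promise an interval, so a reader could be shown two visit means with no statement of how precisely they differ.

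At stake is how informative a supportive result is. The trial collects up to five forms from each randomized subject and promises a comparison. With the summary left open, follow-up means, change scores and adjusted means could each be chosen after the data are seen, and they differ in precision.

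**Working it through.** **Inputs from the documents.** Protocol Section 5.2.1: "A total of 1878 subjects will be randomized to Amulet or Control at up to 150 sites worldwide". Allocation is 1:1 (Section 5.2), so n = 1878 / 2 = 939 per arm. The documents state no SD, correlation, target difference or expected completeness for the EQ-5D-5L, so there is no figure of the plan's own to reproduce.

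**Assumptions.** SD of the index 0.20, the same at baseline and follow-up and in both arms; baseline to follow-up correlation r of 0.3, 0.5 or 0.7; a form from all 939 subjects in each arm.

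**Formulas.** The 95% half-width of the arm difference is 1.96 × SD × √(2f/n). The variance factor f depends on the summary:

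- follow-up means: f = 1
- change from baseline: f = 2(1 − r)
- ANCOVA with baseline as covariate: f = 1 − r²

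**Follow-up means.** 1.96 × 0.20 × √(2/939) = 1.96 × 0.20 × 0.04615 = 0.0181.

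**All three summaries.**

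| r | f, change | half-width, change | f, ANCOVA | half-width, ANCOVA | variance cut, ANCOVA vs follow-up means | width cut |
|---|---|---|---|---|---|---|
| 0.3 | 1.40 | 0.0214 | 0.91 | 0.0173 | 9% | 5% |
| 0.5 | 1.00 | 0.0181 | 0.75 | 0.0157 | 25% | 13% |
| 0.7 | 0.60 | 0.0140 | 0.51 | 0.0129 | 49% | 29% |

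The variance cut is 1 − f and the width cut is 1 − √f. For example, at r = 0.5, √0.75 = 0.866, and 0.0181 × 0.866 = 0.0157.

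**Reading the table.** Change from baseline, the most natural descriptive use of the baseline, gains nothing at r = 0.5 and loses precision below it. ANCOVA is never worse than either alternative, because 1 − r² ≤ 1 and 1 − r² = (1 − r)(1 + r) ≤ 2(1 − r).

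**Sensitivity.** The percentage cuts depend only on r. The absolute half-width for follow-up means scales with the SD: 0.0136 at 0.15 and 0.0226 at 0.25. Missing forms widen all three intervals and, if the same subjects are missing for each summary, leave the ratios unchanged.

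**Chance imbalance.** Under the same assumptions, the baseline means of the two arms may differ by about ±0.018 (95% range). Of an imbalance that large, r times it carries into the unadjusted follow-up difference: 0.5 × 0.018 = 0.009 to 0.7 × 0.018 = 0.013. The unadjusted interval already allows for this on average; adjustment removes most of it in the trial at hand.

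**The case against.** Quality of life is untested and outside the endpoint lists, so nothing here touches a trial conclusion. The unadjusted difference is unbiased under randomization, and its interval is already narrow at this sample size. In absolute terms the gain is about 0.001 to 0.005 of utility at the assumed SD, and the plan names no use for which that would be decisive. Every quantity except 939 per arm is assumed. All of this stands, and it makes the point minor.

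Redaction is a fair caution: an EQ-5D-5L rule could sit in blacked-out text. The point does not depend on its absence, because the method sentence in Section 15 is printed in full and needs at least a cross-reference if another method exists elsewhere.

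Two stronger readings are tempting and are not supported.

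- *The plan discards the baseline value.* Section 15 does not say so. Change from baseline, or baseline tabulated beside each visit, is also descriptive statistics. The plan is silent.
- *The plan limits the comparison to survivors and so hides or reverses a mortality effect.* No form can exist after death, so a summary of subjects alive is the likely default, but no rule states it. Deaths are reported by arm in SAP Sections 5.3 and 6.2, and all-cause death is part of the primary safety endpoint. If death were scored 0 and survivors averaged an assumed 0.80 in both arms, mortality of 7% against 9% would give a difference of 0.80 × (0.93 − 0.91) = 0.016, where the survivors' means show none. With equal mortality it gives zero. That is a different estimand on which statisticians reasonably disagree, and no calculation supports a reversal.

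Section 15 also speaks of device recipients, whereas Section 7.4.2 keeps subjects without an implant in follow-up. Who forms the comparison groups is a separate question.

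**Conclusion.** The point holds as a minor one about precision. Section 15 names descriptive statistics as the only method for a between-arm comparison and states no use of a baseline value that it requires from every subject. The resulting comparison is valid but less precise than it could be. Adjustment would narrow the interval by 13 to 29% at an assumed correlation of 0.5 to 0.7 (equivalent to 1/0.75 = 1.3 to 1/0.51 = 2.0 times the subjects), and by only 5% at 0.3. At an assumed SD of 0.20 with 939 per arm, the half-width of 0.018 becomes 0.016 to 0.013 over the first range and 0.017 at 0.3. Primary and secondary conclusions are unaffected.

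**What to change.** In Protocol Section 15, with a cross-reference from the SAP, keep the descriptive tables and add:

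*The difference between arms in EQ-5D-5L at 45 days and at 6, 12 and 18 months will be estimated with 95% confidence intervals from ANCOVA or a repeated-measures model with baseline EQ-5D-5L as covariate, without hypothesis testing. Results will be labelled as among subjects alive and shown beside the number of deaths by arm at each visit.*

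ANCOVA by visit fits that label most directly. A likelihood-based repeated-measures model treats values after death as missing data, so if it is chosen the text should say how it is to be read. A summary that scores death as 0 is optional and not part of this change.

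The cost is one model and one table, simple imputation for subjects with a missing baseline form, and a named EQ-5D-5L value set for a worldwide trial, or use of the visual analogue scale instead. No new data, visits or subjects are needed.

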16 DOCUMENT RETENTION

Principal investigators will maintain the clinical study documents as required by SJM and applicable regulatory requirements. They will take measures to prevent accidental or premature destruction of these documents. The principal investigator may transfer custody of records to another person/party and document the transfer at the investigational site.

[REDACTED]

The principal investigator must ensure the availability of source documents from which the information on the case report forms was derived.

17 STUDY COMMITTEES

17.1 Steering Committee

A Steering Committee (SC), composed of medical practitioners who are experts in the field of atrial fibrillation, interventional cardiology, neurology, and/or LAA Occlusion, will be appointed by SJM. Specific responsibilities of the members will depend upon the consulting expertise needed by SJM. The SC will advise SJM on trial design, trial conduct, analysis, and reporting of trial results (including publications), as outlined in the SC charter.

17.2 Clinical Event Committee

The Clinical Event Committee (CEC) is a physician group who will review and adjudicate adverse events that occur during the trial, specifically those pertaining to the primary and secondary endpoints. The CEC will be blinded to the treatment group. With respect to review and adjudication of neurological events, events will be captured on the AE and Stroke/TIA assessment eCRFs and will include the NIHSS, mRS, and Barthel index scores (collected at both the time of event and 90 days after the event). Source documentation related to the event will be collected, including brain and echo imaging, for complete review by the CEC. Membership, roles, and responsibilities are defined in the CEC charter.

17.3 Data and Safety Monitoring Board

An independent Data and Safety Monitoring Board (DSMB) will be utilized to advise the sponsor regarding the continuing safety of trial subjects and those yet to be recruited to the trial, as well as the continuing validity and scientific merit of the trial. The DSMB members will not be investigators in the trial.

At any time during the trial, the DSMB may offer opinions or provide formal recommendations concerning aspects of the study that impact subject safety (e.g., safety-related changes or input regarding study-related adverse event rates). An agreed-upon charter between both SJM and the DSMB members will govern the roles and responsibility of this committee.

17.4 Echocardiography Core Lab

An independent Echocardiography Core Laboratory will be utilized to analyze echo imaging, as required, during the trial. Echoes performed during and after the implant procedure, or as necessary and at the request of SJM, will be uploaded to a web-based platform and reviewed by the core lab. Members of the Echocardiography Core Lab will have no affiliation with the Amulet IDE Clinical Trial.

18 INVESTIGATION SUSPENSION OR TERMINATION

18.1 Premature Termination

The sponsor reserves the right to stop the study at any stage, with appropriate written notice to the investigator.

If for any reason SJM suspends or prematurely terminates the trial at an individual investigational site, SJM will inform the responsible regulatory authority, as appropriate, and ensure that the IRB/EC/HREC are notified, either by the principal investigator or by SJM. If the suspension or premature termination was in the interest of safety, SJM will inform all other principal investigators.

If suspension or premature termination occurs, SJM will remain responsible for providing resources to fulfill the obligations from the CIP and existing agreements for following up the subjects enrolled in the clinical study, and the principal investigator or authorized designee will promptly inform the enrolled subjects at his/her investigational site, if appropriate.

18.2 Study Conclusion

The study will be concluded when:

- All sites are closed AND
- The final report generated by SJM has been provided to sites or SJM has provided formal documentation of study closure

19 PUBLICATION POLICY

A Publication Agreement will be signed between the principal investigator and the sponsor either as a separate Publication Agreement or within the Clinical Trial Agreement.

The investigator or site may not publish any information that the sponsor believes to be confidential information. The publication of the initial results of the Amulet IDE trial shall be subject to the review and release of sponsor's publication committee, which shall confer with the site regarding such publication.

Publication guidelines will be followed according to the International Committee of Medical Journal Editors (ICMJE). Upon receiving IDE approval from the FDA, this clinical trial will be registered on ClinicalTrials.gov. A full report of the pre-specified outcomes, regardless of trial results, will be made public through the ClinicalTrials.gov website according to the requirements of Section 801 of the FDA Amendments Act. If this clinical trial is terminated early, SJM will make every effort to hasten the release of the pre-specified outcomes through the ClinicalTrials.gov website.

Appendix A: Abbreviations

Select or add abbreviations used

Abbreviation	Term
--------------	------

ACP	AMPLATZER™ Cardiac Plug
AE	Adverse Event
AF	Atrial Fibrillation
ASA	Atrial Septal Aneurysm
ASD	Atrial Septal Defect
BARC	Bleeding Academic Research Consortium
CA	Competent Authority
CABG	Coronary Artery Bypass Graft
CE	Conformité Européenne
CEC	Clinical Events Committee
CFR	Code of Federal Regulations
CHF	Congestive Heart Failure
CIP	Clinical Investigational Plan
CMS	Centers for Medicare and Medicaid Services
CRF	Case Report Form
CT	Computed Tomography
DFU	Directions for Use
DMP	Data Management Plan
DSMB	Data and Safety Monitoring Board
EC	Ethics Committee
ECG	Electrocardiogram
eCRF	Electronic Case Report Form
EDC	Electronic Data Capture
EP	Electrophysiology
FDA	Food and Drug Administration
GP	General Practitioner
HREC	Human Research Ethics Committee
IB	Investigator Brochure
ICMJE	International Committee of Medical Journal Editors
IDE	Investigational Device Exemption
IFU	Instructions for Use
INR	International Normalized Ratio
IRB	Institutional Review Board
LA	Left Atrium
LAA	Left Atrial Appendage
LAAC	Left Atrial Appendage Closure
LAO	Left Atrial Appendage Occlusion
LVEF	Left Ventricular Ejection Fraction
MI	Myocardial Infarction
MRI	Magnetic Resonance Imaging
mRS	Modified Rankin Scale
NA	Not Applicable
NIHSS	National Institute of Health Stroke Scale
NOAC	Novel Oral Anticoagulant
NSAID	Non-Steroidal Anti Inflammatory Drug

NVAF	Non Valvular Atrial Fibrillation
NYHA	New York Heart Association Classification
OAC	Oral Anticoagulation
PAS	Post-Approval Study
PET	Polyethylene Terephthalate
PFO	Patent Foramen Ovale
PI	Principal Investigator
PMA	Pre-Market Approval
RNT	Randomized Not Treated
SAE	Serious Adverse Event
SAP	Statistical Analysis Plan
SC	Steering Committee
SE	Systemic Embolism
SJM	St. Jude Medical
TEE/TOE	Transesophageal echocardiography
TIA	Transient Ischemic Attack
UCB	Upper Confidence Bound
US	United States
UADE	Unanticipated Adverse Device Effect
WMA	World Medical Association

